## **3.0 PARTICIPANT SELECTION**

A rostered AMC investigator (CTEP-registered physician investigator) must document that each protocol participant meets all stated eligibility criteria. Participating sites must have documentation that each eligibility requirement is satisfied prior to participant enrollment. In compliance with CTEP policy, no exceptions to eligibility criteria will be granted under any circumstance.

### **3.1 Eligibility Criteria**

- 3.1.1 Participants must have measurable cutaneous KS that has been pathologically confirmed by an AMC-approved pathologist. Diagnostic tissue must be available to satisfy the tissue submission requirements at [Appendix V](#) for central pathology review.
- 3.1.2 Participants may not show evidence for ongoing improvement in KS lesions in the 4 weeks prior to enrollment.
- 3.1.3 HIV positive. Documentation of HIV-1 infection by means of any one of the following:
  - HIV-1 RNA detection by a licensed HIV-1 RNA assay demonstrating >1000 RNA copies/mL confirmed by a licensed screening antibody and/or HIV antibody antigen combination assay;
  - Any licensed HIV screening antibody and/or HIV antibody/antigen combination assay confirmed by a second licensed HIV assay such as a HIV-1 Western blot confirmation or HIV rapid multispot antibody differentiation assay.

Note: The term “licensed” refers to a kit that has been certified or licensed by an oversight body within the participating country and validated internally.

WHO (World Health Organization) and CDC (Centers for Disease Control and Prevention) guidelines mandate that confirmation of the initial test result must use a test that is different from the one used for the initial assessment. A reactive initial rapid test should be confirmed by either another type of rapid assay or an E/CIA that is based on a different antigen preparation and/or different test principle (e.g., indirect versus competitive), or a Western blot or a plasma HIV-1 RNA viral load.

- 3.1.4 Age  $\geq$  18 years.

Because no dosing or adverse event data are currently available on the use of Pomalidomide in participants  $<18$  years of age, children are excluded from this study.

- 3.1.5 Eastern Cooperative Oncology Group (ECOG) performance status  $\leq 2$  (Karnofsky Performance Status (KPS)  $\geq 50$ , see [Appendix II](#)).
- 3.1.6 Life expectancy  $\geq 12$  weeks.
- 3.1.7 Participants must have organ and marrow function within the following parameters, unsupported by hematopoietic growth factors within 7 days prior to enrollment:
  - Hemoglobin  $\geq 8$  g/dL

- Absolute neutrophil count (ANC):  $\geq 1,000 \text{ cells/mm}^3$  ( $1.0 \times 10^9/\text{L}$ )
- Platelets:  $\geq 75,000 \text{ cells/mm}^3$  ( $75.0 \times 10^9/\text{L}$ )
- Total bilirubin:  $\leq 1.5$  times the upper limit of normal (ULN), unless the participant is receiving an antiretroviral drug known to be associated with increased bilirubin, in which case the direct fraction should be  $\leq 2$  times the ULN.
- Serum AST (SGOT) / ALT (SGPT):  $\leq 2.5 \times \text{ULN}$
- Estimated or measured creatinine clearance  $\geq 60 \text{ mL/minute}$  ( $1.00 \text{ mL/s}$ ) (serum creatinine  $\leq 2.0 \text{ mg/dL}$  /  $176.8 \mu\text{mol/L}$ )

3.1.8 Currently receiving local standard of care ART for  $\geq 12$  weeks, with HIV viral load  $\leq 400$  copies/mL within the preceding 12 weeks prior to enrollment.

Participants are required to be on antiretroviral regimens that are in accordance with the current International AIDS Society guidelines concurrently with chemotherapy. Excepting agents containing zidovudine, which is prohibited, the specific agents are at the discretion of the Investigator and the use of investigational ART agents currently available on an expanded access basis is allowed.

3.1.9 A FCBP is a female who has achieved menarche at some point, is  $< 60$  years of age, and who meets one of the following criteria:

- 1) has not undergone a hysterectomy or bilateral oophorectomy, or
- 2) has not been naturally postmenopausal (amenorrhea following cancer therapy does not rule out childbearing potential) for at least 24 consecutive months (i.e., has had menses at any time in the preceding 24 consecutive months), or
- 3) does not have a serum or plasma FSH  $>40 \text{ mIU/mL}$  and a history of amenorrhea  $\geq 1$  year

FCBP must have a negative serum or urine pregnancy test with a sensitivity of at least  $25 \text{ mIU/mL}$  within 14 days prior to enrollment and again within 24 hours of starting pomalidomide and must either commit to continued abstinence from heterosexual intercourse or, if complete abstinence cannot be assured, they must begin TWO acceptable methods of birth control, including one of the following highly effective, long-acting methods, DepoProvera, an intrauterine device (IUD), an implant\*, or bilateral tubal ligation, if it can be verified that the procedure was performed, and one additional effective method AT THE SAME TIME, at least 28 days before she starts taking pomalidomide. FCBP must also agree to ongoing pregnancy testing.

\* **NOTE:** Implants containing levonorgestrel and etonogestrel are prohibited in women receiving efavirenz, as drug interactions will render the implants ineffective.

Men must agree to use a latex condom during sexual contact with a FCBP even if they have had a vasectomy.

All participants must be counseled at a minimum of every 28 days about pregnancy

precautions and risks of fetal exposure. Serum or urine pregnancy testing will be repeated in FCBP, and must be negative, within 24 hours of starting each new cycle of pomalidomide. See [Appendix VII](#): Pomalidomide Risks of Fetal Exposure, Pregnancy Testing Guidelines and Acceptable Birth Control Methods, AND also [Appendix VIII](#): Pomalidomide Education and Counseling Guidance Document for further instructions.

- 3.1.10 Able to take aspirin daily as prophylactic anticoagulation as described in [Section 4.3](#).
- 3.1.11 Ability to understand and the willingness to sign a written informed consent document.

## 3.2 Exclusion Criteria

Participants who do not fulfill the criteria as listed in [Section 3.1](#) above, are ineligible. Additionally, the presence of any of the following conditions will exclude a participant from study enrollment:

- 3.2.1 Participants who are receiving any other investigational agents (except as permitted in [3.1.8](#)).
- 3.2.2 Any prior use of thalidomide, lenalidomide, or pomalidomide.
- 3.2.3 History of allergic reactions attributed to compounds of similar chemical or biologic composition to pomalidomide.
- 3.2.4 Participants who have visceral disease requiring cytotoxic chemotherapy (i.e., pulmonary KS, symptomatic gastrointestinal KS) or in whom the omission of conventional cytotoxic chemotherapy is not consistent with the local standard of care. KS-related lymphedema is permitted.
- 3.2.5 Use of agents containing zidovudine (including Combivir® and Trizivir®) are prohibited. In order to be eligible, participants taking zidovudine must change to a different regimen at least 7 days prior to therapy initiation. Changes to ART therapy during the study may be made if medically necessary (toxicity, failure of regimen, etc.).

Use of medications or substances that are strong inhibitors of CYP1A2, which include amiodarone, cimetidine, fluoroquinolones (e.g., ciprofloxacin, enoxacin), fluvoxamine, and ticlopidine is prohibited.

Co-administration of efavirenz, an inhibitor of CYP1A2, with strong inhibitors of CYP3A4 and P-glycoprotein (P-gp) is prohibited. See [Appendix VI](#) for a list of all prohibited medications on this trial.

Use of erythropoietin is prohibited.

Co-administration of corticosteroids greater than doses required for treatment of adrenal insufficiency is prohibited.

Because the lists of these agents are constantly changing, it is important to regularly consult frequently updated medical references.

- 3.2.6 Uncontrolled intercurrent illness including, but not limited to, ongoing or active

infection for which the participant has not completed at least 14 days of therapy prior to study enrollment and/or is not clinically stable; symptomatic congestive heart failure; unstable angina pectoris; cardiac arrhythmia; or psychiatric illness/social situations that, in the opinion of the investigator, would limit compliance with study requirements.

- 3.2.7 Pregnant women are excluded from this study because pomalidomide is a thalidomide analog with the potential for teratogenic or abortifacient effects. Because there is an unknown but potential risk for adverse events in nursing infants secondary to treatment of the mother with pomalidomide, breastfeeding should be discontinued if the mother is treated with pomalidomide.
- 3.2.8 Specific KS therapy, including cytotoxic chemotherapy but not including ART, within the past 4 weeks.
- 3.2.9 Use of other anticancer treatments or agents within the past 4 weeks.
- 3.2.10 History of malignant tumors other than KS, unless:
  - In complete remission for  $\geq$  1 year, or
  - Completely resected basal cell carcinoma, or
  - In situ squamous cell carcinoma of the cervix or anus.
- 3.2.11 Grade  $>$  1 peripheral neuropathy.
- 3.2.12 History of myocardial infarction (MI), cerebrovascular accident, or venous or arterial thromboembolism, unless line-related thrombosis without embolus occurring greater than 1 year prior to study entry.
- 3.2.13 Known procoagulant disorder including prothrombin gene mutation 20210, antithrombin III deficiency, protein C deficiency, protein S deficiency and antiphospholipid syndrome but not including heterozygosity for the Factor V Leiden mutation or the presence of a lupus anticoagulant in the absence of other criteria for the antiphospholipid syndrome.
- 3.2.14 Any condition, including the presence of current laboratory abnormalities or other factor that, in the opinion of the investigator, places the participant at unacceptable risk if they were to participate in the study or confounds the ability to interpret data from the study.

### **3.3 Number of Participants to be Enrolled**

- 3.3.1 Proposed sample size

This study will enroll 26 participants.

- 3.3.2 Accrual rate

Approximately two participants per month.

### **3.4 Participant Enrollment Procedures**

This study will be available for enrollment at the AMC African sites. Sites must have this protocol approved by their Institutional Review Boards (IRB), national regulatory authority (where required) and be registered with the AMC Operations and Data

Management Center (ODMC) before they may enroll participants. Protocol registration instructions and forms will be made available on the AMC Operations website ([www.AIDSCancer.org](http://www.AIDSCancer.org)). Participating sites may not order study drugs until protocol registration with the AMC ODMC is complete.

### 3.4.1 Registration for Screening

After an informed consent form has been signed by the participant, the participant must be registered for screening (AMC-100 Screening Segment) on-line via the AMC Advantage eClinicalSM Internet Data Entry System. After successful registration into the screening segment, the participant will receive an eleven-digit participant ID and will then enter the screening process. Participants will be enrolled on-line via the AMC Internet Data Entry System no more than 42 days prior to the initiation of treatment. Once the eligibility checklist is submitted, a system-generated confirmation will be sent to the site staff, AMC ODMC, and Protocol Chair upon successful registration.

Please reference the AMC-100 MOP for additional details regarding the required tests prior to enrollment in the screening segment.

If the on-line system is inaccessible for Screening Registration (Screening Segment), the site should notify the AMC ODMC via email at [[contact]](mailto:[contact]) or via phone at [name] for further instructions. Please refer to the AMC-100 MOP for additional instructions.

### 3.4.2 Treatment Segment Enrollment

After all required eligibility assessments are complete, the participating site will complete the protocol-specific eligibility checklist and enroll the participant into the AMC-100 Treatment Segment on-line via the AMC Advantage eClinicalSM Internet Data Entry System. The participating site will ensure the participant meets all eligibility criteria prior to completing the protocol-specific eligibility checklist. Participants will be enrolled on-line via the AMC Internet Data Entry System no more than 1 week prior to the initiation of treatment (enrollment 1 day prior to or on the day of treatment is strongly encouraged). Once the eligibility checklist is submitted, a system-generated confirmation will be sent to the site staff, AMC ODMC, and Protocol Chair upon successful registration.

If the on-line system is inaccessible for Treatment Enrollment Registration (Treatment Segment), the site should notify the AMC ODMC via email at [[contact]](mailto:[contact]) or via phone at [contact] for further instructions.

## **4.0 TREATMENT PLAN**

### **4.1 Agent Administration**

Pomalidomide will be administered on an outpatient basis. Reported adverse events and potential risks for pomalidomide are described in [Section 6.0](#). Appropriate dose modifications for pomalidomide are described in [Section 5.0](#). No investigational or commercial agents or therapies other than those described below may be administered with the intent to treat the participant's malignancy.

**NOTES: At all times, when dispensing study drug, research center personnel will review the instructions, printed on the packaging, with participants. The participant will be requested to maintain a medication diary of each dose of medication ([Appendix IV](#)). The medication diary will be returned to clinic staff at the end of each course.**

**The site will be required to document study agent return by participant in source documents. Non-compliance with study agent administration should be noted at the time of diary collection and the participant should be instructed again regarding dosing instructions.**

#### **4.1.1 Pomalidomide**

Each cycle of treatment includes administration of 21 doses of pomalidomide during a 4-week period, administered on days 1-21 of a 28-day cycle ( $\pm$  2 days). The maximum duration of treatment is twelve 4-week cycles. Pomalidomide will be administered on a daily schedule at approximately the same time each day. At each dose administration, the capsule number corresponding to the appropriate dose level of pomalidomide is to be swallowed whole with a glass of water (150-200 mL). Participants should be instructed not to bite or chew on the capsule. In case of breakage of the capsule in the oral cavity, an additional glass of water should be taken immediately. Participants will be instructed to fill out a medication diary to record medication administered each day.

Study medications will be dispensed at study entry (day 1) and at each subsequent study visit at the start of a new cycle. Participants will be instructed to return any unused study medication and medication containers at each study visit and bring their completed medication diary to each study visit. At each visit, medication diaries and returned medication counts will be performed and participants will undergo repeat counseling and medication adherence assessments. Participants will receive up to six cycles of pomalidomide if they have stable disease, or up to 12 cycles of pomalidomide if they show a complete or partial tumor response, unless they develop unacceptable toxicity or meet another protocol-defined reason for treatment discontinuation.

Only enough pomalidomide for one cycle of treatment will be provided to the participant at the start of each cycle.

If participants miss a dose, the dose may still be taken up to 12 hours after the time they normally would take it. If more than 12 hours have elapsed, the dose should be skipped. Take the next dose at the usual time. Participants should not take 2 doses to make up for the one they missed. Participants who take more than the prescribed

dose of pomalidomide should be instructed to contact the study staff immediately and to seek emergency medical care if needed.

#### 4.1.2 Pomalidomide dosage levels

Eligible participants will begin pomalidomide therapy at dose level 1, 4 mg/day on days 1-21 of each 28-day cycle.

Dose level -1, 3 mg/day on days 1-21 of each 28-day cycle, is provided for participants entered on dose level 1 who require dose reduction.

Safety and the need for dose reduction will be continuously monitored by the protocol team.

The following table shows the number of participants who require dose reduction based on first cycle adverse events that are needed for the starting dosage level to be reduced to 3 mg/day in subsequent participants.

**Table 4-1. Criteria for Dose Reduction**

No. of participants enrolled	More than X participants who required dosage reduction due to first cycle DLTs
7-8	2
9-14	3
15-20	4
21-26	5

This table is based on the probability of observing  $\geq x$  participants who require AE-related dosage reductions is  $< 0.05$ . if the underlying proportion of participants who require dosage reductions due to adverse events (AE) is 0.10.

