#### 10.1.2 Statistical power calculation

To test the null hypothesis that the ORR = 0.10 against the alternative that it is 0.30 with pomalidomide monotherapy at the one-sided 0.10 significance level with power of 0.90 will require 30 participants. The following stopping rule is based on stopping when the probability of observing more than x dose-limiting toxicities (DLTs) in the first cycle, as defined in [Section 4.2](#), is less than 0.05 with an underlying first cycle DLT rate of 0.10.

Since the enrollment is planned to close at the end of 2023, the target number of enrollment (30 participants) may not be achieved. It is expected that 26 participants will be able to be enrolled before study enrollment closes. As an illustration of statistical power based on the assumption that the null hypothesis that the ORR = 10% against the alternative that it is 30% with pomalidomide monotherapy at the one-sided 10% significance level, statistical power of 87.5% can be achieved with 26 participants. The following stopping rule is based on stopping when the probability of observing more than x DLTs in the first cycle, as defined in [Section 4.2](#), is less than 5% with an underlying first cycle DLT rate of 10%.

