#### 10.1.3 Stopping Rules

**Table 10-1. Stopping Rules for Dose-limiting Toxicity**

N	More Than X Participants with DLTs
7-8	2
9-14	3

15-20	4
21-26	5

The study team will monitor trial safety and the safety stopping rule using the procedures outlined in the DMSP. The AMC Data and Safety Monitoring Board (DSMB) will perform an annual review of trial safety to evaluate whether DLTs have occurred and that the safety stopping rule has been followed appropriately. Accrual will not be paused for these reviews because they are confirmatory to the study team's process, unless the safety rule is invoked by the study team's review.

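### Table 4-1: the limits are right, but the footnote's inequality contradicts the header, and choosing the row by participants enrolled can delay the starting-dose trigger

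*Combined protocol and SAP*

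**What the plan says.** Section 4.1.2 introduces Table 4-1 as the number of participants needing dose reduction for first-cycle events that causes the "starting dosage level to be reduced to 3 mg/day in subsequent participants". The table has two columns. The first is headed "No. of participants enrolled" and the second "More than X participants who required dosage reduction due to first cycle DLTs". The limits X are 2 (7-8 participants), 3 (9-14), 4 (15-20) and 5 (21-26).

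The footnote gives the basis: "This table is based on the probability of observing", followed by "\geq x$ participants who require AE-related dosage reductions is" (the at-least sign), with the probability required to be below 0.05 when the underlying proportion is 0.10.

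Section 10.1.2 describes the parallel DLT rule as "stopping when the probability of observing more than x DLTs in the first cycle" is below 5% at a 10% rate. Table 10-1 has the same four limits under "More Than X Participants with DLTs", and labels its first column only N.

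Other sections bear on the denominator:
- Section 4.2 places DLTs in the first cycle and allows replacement of participants who leave that period for reasons unrelated to the drug.
- Section 3.4.2 allows enrollment up to a week before treatment.
- Section 3.3.2 expects about two participants per month.

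**The concern.** The header and the footnote give different inequalities for the same threshold. A team that took the footnote as the rule and acted at X, not above X, would trigger far more often than intended when the true rate is 10%.

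Separately, a participant enrolled today has no complete first-cycle outcome for 28 days, plus any gap before the first dose, yet already counts in choosing the row. Suppose three events occur among 8 participants with known outcomes. That exceeds the limit of 2. If a ninth participant was enrolled before the third event became known, the limit is 3 and nothing triggers. The error can only run towards not triggering, and meanwhile further participants start at the level in question.

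**Working it through.** **Inputs.** Limits X, reference rate 0.10 and bound 0.05 from Table 4-1; accrual of about two per month from Section 3.3.2; a 28-day cycle from Section 4.1.1. The documents do not give the number of participants pending at a look, so a range of 1 to 4 is assumed.

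**Step 1: reproduce the limits.** For n participants, P(more than X) = sum over k = X+1 to n of C(n,k) × 0.1^k × 0.9^(n-k).

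Example, n = 8, X = 2: P(0) = 0.9^8 = 0.4305; P(1) = 8 × 0.1 × 0.9^7 = 0.3826; P(2) = 28 × 0.01 × 0.9^6 = 0.1488. So P(more than 2) = 1 - 0.9619 = 0.0381, and P(2 or more) = 0.0381 + 0.1488 = 0.1869.

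Range over each row:

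| n | X | P(more than X) | P(X or more) |
|---|---|---|---|
| 7-8 | 2 | 0.0257-0.0381 | 0.1497-0.1869 |
| 9-14 | 3 | 0.0083-0.0441 | 0.0530-0.1584 |
| 15-20 | 4 | 0.0127-0.0432 | 0.0556-0.1330 |
| 21-26 | 5 | 0.0144-0.0399 | 0.0522-0.1118 |

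P(more than X) is below 0.05 at all 20 values of n. P(X or more), which is the same as P(more than X-1), is above 0.05 at all 20. So each tabulated X is the smallest that meets the bound under 'more than', and none meets it under 'at least'.

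**Step 2: does an enrolled denominator breach the bound?** With n enrolled and e ≤ n outcomes known, the limit is X(n). P(more than X(n) among e) cannot exceed P(more than X(n) among n), which is below 0.05. So it does not.

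**Step 3: single looks at the row boundaries, assuming two pending.** P(exceeding the limit) with the row chosen by known outcomes, then by enrollment:

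| Enrolled / known | Limit, known → enrolled | True rate 0.10 | True rate 0.30 |
|---|---|---|---|
| 9 / 7 | 2 → 3 | 0.0257 → 0.0027 | 0.353 → 0.126 |
| 15 / 13 | 3 → 4 | 0.0342 → 0.0065 | 0.579 → 0.346 |
| 21 / 19 | 4 → 5 | 0.0352 → 0.0086 | 0.718 → 0.526 |

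**Step 4: over the whole trial.** Let f_n(k) be the probability of k events among n known outcomes with no trigger so far. Then f_n(k) = (1-p) f_(n-1)(k) + p f_(n-1)(k-1). At each step, mass with k above the limit for min(n+m, 26) enrolled is removed and added to the trigger probability, where m is the number pending. Looks start at 7 enrolled.

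| m pending | p = 0.10 | p = 0.20 | p = 0.30 |
|---|---|---|---|
| 0 | 0.0880 | 0.5168 | 0.8762 |
| 1 | 0.0751 | 0.4936 | 0.8669 |
| 2 | 0.0646 | 0.4741 | 0.8591 |
| 3 | 0.0565 | 0.4583 | 0.8527 |
| 4 | 0.0504 | 0.4463 | 0.8477 |

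**Step 5: events counted as they occur.** This was simulated with one enrollment every 14 days and event times uniform over the cycle (both assumptions). Enrolled against known denominators gave about 51% against 53% at a 20% rate, and about 87% against 88% at 30%.

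**Step 6: acting at X instead of above X.** The Step 4 recursion with m = 0 and every limit lowered by one gives 0.279 at p = 0.10, against 0.088.

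**The case against.** The strongest reply is that nothing operative is wrong. The header, Section 10.1.2 and Table 10-1 all say more than X, and the limits satisfy the 0.05 bound on that reading at every n. The header uses a capital X and the footnote a lower-case x. If x silently means the triggering count X+1, the footnote is true. The 27.9% from Step 6 belongs to a rule that only a literal reading of the footnote would produce. All of this stands, and it makes the inequality a wording contradiction and not a calculation error. But nothing in the section says that x means X+1.

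On the denominator, Section 4.1.2 says safety is monitored continuously, so events may count as they arise and the loss is then small (Step 5). Under the header's definition, Table 10-1 also counts every participant with a DLT, including those without a dose reduction, so at the same N it is crossed no later than Table 4-1. That limits the separate consequence, although Table 10-1 leaves its own N undefined.

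This version is dated 04DEC2023, and its summary of changes says the last participant had to begin treatment by December 1, 2023. Little prospective effect on starting doses remains. The wording still matters for reporting whether the trigger was met.

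Three stronger readings might be inferred, and the documents do not support them:
- That the trigger departs from its own criterion. The rule in the header meets the criterion at all 20 values of n.
- That pending participants push the tail above 0.05. They can only lower it (Step 2).
- That replaced participants inflate the row count. Section 4.2 allows replacement but does not say whether those replaced stay in the count.

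**Conclusion.** Two wording defects hold, both minor. The footnote's inequality, read with the tabulated X, is false in every row and contradicts the header; the limits themselves are correct. Selecting the row by enrollment makes the trigger less sensitive or later near 9, 15 and 21 enrolled, with no breach of the stated bound.

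Over the trial, with 1 to 4 participants always pending, the loss is 2.3 to 7.1 percentage points at a true 20% rate (51.7% to between 49.4% and 44.6%). At 30% it is 0.9 to 2.9 points (87.6% to between 86.7% and 84.8%). If events count as they occur, the loss is about 1 to 2 points. These sizes rest on the assumed number pending and, for the last figure, on assumed event timing. The single-look losses in Step 3 are larger, but they apply only at the boundaries and are partly recovered at later looks.

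**What to change.** Reconcile the footnote's inequality with the Table 4-1 header and with Section 10.1.2; the tabulated limits follow from the 0.05 bound only under 'more than'.

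Define the Table 4-1 denominator, and N in Table 10-1, as participants who have completed cycle 1 or already had the counted event. For Table 10-2, define N by that table's own event, Grade 3 or higher toxicity. A DLT-based definition there would leave a participant with a non-DLT Grade 3 event, still in cycle 1, in the numerator but not in the denominator. State in all three tables whether replaced participants are counted.

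The cost is a few phrases. No limit, dose or clinical rule changes.
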